8.5.2 CCI

CCI

Table 8-6

CCI

CCI

8.5.3 Other Assessments

8.5.3.1 Exploratory assessments

CCI

9 Study discontinuation and completion

9.1 Discontinuation and completion

9.1.1 Study treatment discontinuation and study discontinuation

Discontinuation of study treatment for a participant occurs when study treatment is stopped earlier than the protocol planned duration and can be initiated by either the participant or the investigator.

The investigator must discontinue study treatment for a given participant if, he/she believes that continuation would negatively impact the participant's well-being.

Study treatment must be discontinued under the following circumstances:

- Participant/guardian decision
- Pregnancy
- Use of prohibited treatment (see [Section 6.2.3](#))
- Use of IV rescue medication (see [Section 6.2.1](#))
- Any situation in which study participation might result in a safety risk to the participant (eg., see [Section 16.1](#), [Section 16.2](#))
- Diagnosed with COVID-19 infection

If discontinuation of study treatment occurs, then investigator should make a reasonable effort to understand the primary reason for the participant's premature discontinuation of study treatment and record this information.

Participants who discontinue study treatment or who decide they do not wish to participate in the study further should NOT be considered withdrawn from the study UNLESS they withdraw their consent (see 'Withdrawal of Informed Consent' section). **Where possible, they should return for the assessments indicated** in the Assessment Schedule. If they fail to return for these assessments for unknown reasons, every effort (e.g. telephone, e-mail, letter) should be made to contact the participant/pre-designated contact as specified in the lost to follow-up section. This contact should preferably be done according to the study visit schedule.

If the participant cannot or is unwilling to attend any visit(s), the site staff should maintain regular telephone contact with the participant, or with a person pre-designated by the participant. This telephone contact should preferably be done according to the study visit schedule.

After study treatment discontinuation, at a minimum, in abbreviated visits, the following data should be collected at clinic visits or via telephone/email contact:

- New / concomitant treatments
- Adverse Events / Serious Adverse Events

The investigator must also contact the IRT to register the participant's discontinuation from study treatment.

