	
4. known or suspected to be HIV-1 positive and/or receiving antiretroviral treatment
 
5. malignancy of any organ system (other than localized basal cell carcinoma of the skin or in situ cervical cancer), treated or untreated, within the past 5 years, regardless of whether there is evidence of local recurrence or metastases
 
6. known or suspected cases of active infections or concurrent febrile illness such as TB, Typhoid, COVID-19 etc.
 
Additional exclusion criteria are as follows:
 
Exclusion criteria for Cohort 1:
 
-ALT > 5 x the upper limit of normal range (ULN), regardless the level of total bilirubin
 
-Total bilirubin is > 3 mg/dL
 
-Body weight of < 35 kg or >75 kg
 
Exclusion criteria for Cohort 2:
 
-Body weight of < 35 kg or >75 kg
 
-Participants diagnosed as moderately severe malaria due to repeated vomiting without presence of any of the symptoms of severe malaria
 
Exclusion criteria for Cohorts 3 to 5:
 
-Body weight of < 5 kg
 
-Participants diagnosed as moderately severe malaria due to repeated vomiting without presence of any of the symptoms of severe malaria

Study treatment	
Study treatments:
 
 • Cipargamin 10 mg/ml and/or 15mg/ml vial (investigational drug) for intravenous administration • Artesunate 60 mg vials (control drug) for intravenous administration 
Study treatment will be followed by a full course of oral standard of care antimalarial.
 
Additional treatments:
 
 • Oral standard of care: artemether/lumefantrine • Rescue medication: IV artesunate
Treatment of interest	IV cipargamin versus IV artesunate
Efficacy assessments	
 • Parasitemia • Clinical outcome as measured as normalization of signs of severe malaria
Pharmacokinetic assessments	Standard PK parameters of cipargamin and alpha-1-acid glycoprotein level over time
Key safety assessments	
 • Adverse event monitoring • Physical examination • Vital signs • Laboratory assessments of blood and urine • ECG assessment

Other assessments	

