Parenteral artesunate is the first line treatment for severe malaria as recommended by [WHO 2015](#). All participants will be treated with IV cipargamin or IV artesunate for at least 24 h (minimum of 2 doses of IV cipargamin and 3 doses of IV artesunate) and until oral therapy can be tolerated. IV therapy will be followed by oral antimalarial therapy as per standard treatment practice. The oral treatment is a 3-day course of Coartem to ensure complete elimination of parasites in participants.

The open label design is chosen since the dosing frequency and method of administration of test drug and comparator is not similar. Hence, blinding the treatment would require multiple placebo injections in a double dummy design which is ethically not acceptable considering the severity of the disease and need for inclusion of pediatric participants. Furthermore, the risk of bias arising out of the open-label design is minimized due to the objectivity of the primary endpoint, which is based on reduction of parasitemia.

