6.1.4 Treatment duration

Participants will be treated with IV cipargamin (KAE609) once daily for at least 24 hours (2 doses) and a maximum of 48 hours (3 doses). Participants requiring prolonged IV treatment will be switched to IV artesunate and treated according to local practice. Participants in control arms will receive IV artesunate for at least 24 hours (3 doses) and for a maximum of 7 days if necessary as per label or until oral Coartem (standard of care) can be tolerated, whichever is earlier (see criteria for switch to oral therapy in [Section 6.1.2.1](#)).

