6.7.2 Instruction for prescribing and taking study treatment

Cipargamin (KAE609)

IV cipargamin should be administered for a minimum of 24 hours (2 doses), regardless of the participant's ability to tolerate oral medication earlier. After at least 2 doses or a maximum of 3 daily doses of IV cipargamin, the participant should be switched to a complete treatment course of oral Coartem or rescue medication (see sections [Section 6.1.2.1](#), [Section 6.2.1](#)).

Preparation:

The specified dose of cipargamin should be prepared by withdrawing the calculated volume from the 2ml vial containing either 10mg/ml or 15mg/ml KAE609. For dose preparation refer to the Pharmacy Manual.

As described in [Section 4.2](#) doses in Cohorts 3-5 might be adjusted during the trial to reach optimal exposure in the different age groups.

Administration

Cipargamin should be administered as a slow bolus injection over two minutes by the intravenous route. It should not be administered intramuscularly or subcutaneously.

Artesunate

IV artesunate should be administered for a minimum of 24 hours (3 doses), regardless of the participant's ability to tolerate oral medication earlier. After at least 24 hours of IV artesunate, the participant should be switched to a complete treatment course of oral Coartem (see [Section 6.1.2.1](#)).

Artesunate should be prepared according to the supplied instructions in label for IV administration and injected by the IV route as a bolus over 1-2 minutes.

Coartem

Coartem® should be administered according to the supplied label and with food/drink (broth, sweetened condensed milk, etc.) as appropriate.

All dosages prescribed and dispensed to the participant during the study must be recorded on the Dosage Administration Record (DAR) CRF.

All kits of study treatment assigned by the IRT will be recorded in the IRT.

7 Informed consent procedures

Eligible participants may only be included in the study after parents, legal guardians or caregivers provide written (witnessed, where required by law or regulation), Institutional Review Board/Independent Ethics Committee/ Research Ethics Board (IRB/IEC/REB)-approved informed consent.

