10.1 Definition of adverse events and reporting requirements

10.1.1 Adverse events

An adverse event (AE) is any untoward medical occurrence (e.g. any unfavorable and unintended sign [including abnormal laboratory findings], symptom or disease) in a participant or clinical investigation participant after providing written informed consent for participation in the study. Therefore, an AE may or may not be temporally or causally associated with the use of a medicinal (investigational) product.

The investigator has the responsibility for managing the safety of individual participant and identifying adverse events.

Novartis qualified medical personnel will be readily available to advise on trial related medical questions or problems.

The occurrence of adverse events must be sought by non-directive questioning of the participant at each visit during the study. Adverse events also may be detected when they are volunteered by the participant during or between visits or through physical examination findings, laboratory test findings, or other assessments.

Adverse events must be recorded under the signs, symptoms, or diagnosis associated with them, accompanied by the following information (as far as possible) (if the event is serious refer to [Section 10.1.2](#)):

1. The Common Toxicity Criteria (CTC) AE grade version 5

Adverse events will be assessed and graded according to the Common Terminology Criteria for Adverse Events (CTCAE) version.

2. its relationship to the study treatments (ie IV cipargamin or IV artesunate). If the event is due to lack of efficacy or progression of underlying illness (i.e. progression of the study indication) the assessment of causality will usually be 'Not suspected.' The rationale for this guidance is that the symptoms of a lack of efficacy or progression of underlying illness are not caused by the trial drug, they happen in spite of its administration and/or both lack of efficacy and progression of underlying disease can only be evaluated meaningfully by an analysis of cohorts, not on a single participant
3. its duration (start and end dates) or if the event is ongoing, an outcome of not recovered/not resolved must be reported
4. whether it constitutes a SAE (see [Section 10.1.2](#) for definition of SAE) and which seriousness criteria have been met
5. action taken regarding with study treatment

All adverse events must be treated appropriately. Treatment may include one or more of the following:

- Dose not changed

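### Section 9.1.1 stops control IV artesunate as well as cipargamin for COVID-19 or prohibited-drug use, and that arm has no other permitted IV antimalarial

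*Protocol*

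**What the plan says.** Protocol 9.1.1 opens its list of mandatory stops with "Study treatment must be discontinued under the following circumstances". Two of the entries are use of a prohibited treatment, with a pointer to 6.2.3, and "Diagnosed with COVID-19 infection". Neither is qualified by arm, severity or doses already given. The same section says that participants who stop treatment "should NOT be considered withdrawn from the study UNLESS they withdraw their consent".

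Control artesunate is study treatment. The Protocol summary lists "Artesunate 60 mg vials (control drug) for intravenous administration" under that heading, with Coartem and rescue artesunate placed separately as additional treatments. Section 10.1.1 asks for each adverse event "its relationship to the study treatments (ie IV cipargamin or IV artesunate", and SAP 2.1.1 names both IV drugs as the randomized treatments.

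On dosing, Protocol 4.1 says "All participants will be treated with IV cipargamin or IV artesunate for at least 24 h", and 6.7.2 says "IV artesunate should be administered for a minimum of 24 hours (3 doses", the third dose falling at 24 h. On alternatives, 6.2.1 rules out any other IV antimalarial as rescue in the artesunate arm, Table 6-6 prohibits other antimalarials except as rescue, and SAP 1.1 confirms that the arm has no rescue medication.

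**The concern.** Neither trigger is in itself a reason to stop artesunate. A positive COVID-19 result, or one dose of an antibiotic on the Table 6-6 list such as azithromycin or doxycycline, does not remove the need for parenteral treatment of severe malaria. A cipargamin participant who needs further IV treatment has somewhere to go, because 6.1.4 and 6.2.1 provide for IV artesunate. The artesunate participant has no such route.

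The stake is patient safety, not the analysis. A site that follows 9.1.1 to the letter withdraws the only permitted IV antimalarial from a patient who may be unable to swallow. No sample size, power figure or confidence interval in the plan depends on the point.

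**Working it through.** The plan gives no figure to reproduce, so the check sets the texts side by side, with simple dose arithmetic.

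**1. Does the rule reach the control arm?** Yes. The Protocol summary, 10.1.1 and SAP 2.1.1 each place IV artesunate within study treatment, and one glossary definition expressly includes controls. The prohibited-drug entry points to 6.2.3, which has a separate list for the artesunate arm (Table 6-6).

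**2. Is there a permitted replacement?** Not an IV one. Section 6.2.1 excludes other IV rescue on the ground that artesunate is the only standard of care, which presumes that artesunate continues. Sections 4.1.1 and 6.2.2 and Table 6-6 bar additional antimalarials except as rescue. Section 6.5.1 does not permit interruption for an individual participant, so a pause and restart is not offered either.

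**3. Does other text override the stop?**
- Protocol 4.2 says that in severe cases total IV duration follows the participant's condition and the artesunate prescribing information. This covers artesunate alone, but it concerns duration and does not refer to 9.1.1.
- Section 6.2.2 sends doubts about concomitant drugs to the sponsor, but on whether participation should continue, and only when time allows.
- Section 14.1 expects immediate action for safety, but treats it as a possible deviation.
- Section 9.2 requires follow-up care for participants withdrawn from the study. Tables 12-1 and 12-2 give COVID-19 as an example of leaving the study, yet 9.1.1 separates stopping treatment from withdrawal.

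Each of these softens the rule. None cancels the mandatory wording.

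**4. How does the protocol handle a comparable case?** The 9.1.1 list cites Section 16.1 as an example of a safety stop. In Table 16-2, ALT above 20 x ULN stops cipargamin with a switch to IV artesunate, while IV artesunate may continue on the investigator's benefit-risk assessment. That arm-specific wording is what 9.1.1 lacks.

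**5. What would a literal stop mean for dosing?** Artesunate is due at 0, 12 and 24 h (Table 6-2), and the first recommended oral switch is at 48 h (6.1.2.1).
- Stop between 0 and 12 h: 1 of 3 doses given; 48 - 0 = 48 h from last dose to the switch point.
- Stop between 12 and 24 h: 2 of 3 doses given; 48 - 12 = 36 h.
- Stop after the 24 h dose: 3 of 3 doses given; oral treatment at 48 h is on the usual schedule if tolerated.

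The first two intervals assume that Coartem is not started before 48 h and is tolerated then.

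**6. Who is exposed?** SAP 1.1 reports Cohorts 1 and 2 as complete. Planned artesunate numbers in Cohorts 3, 4 and 5 are 38 + 38 + 20 = 96. The documents give no trigger rate, so no expected count follows.

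**The case against.** The strongest reply is that this is a wording point that few sites would ever meet. Known or suspected COVID-19 is an entry exclusion (5.2), the visible rows of the assessment schedules show no COVID-19 test, and a gap in dosing can arise only in the first 24 h. Section 4.2 ties IV duration to clinical need, and most investigators would go on treating. Rarity stands and limits the size of the point. The reliance on 4.2 does not, because a general statement about duration does not displace a mandatory stop.

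A reader might infer more than the documents support:
- *That 9.1.1 contradicts the three-dose minimum.* Section 9.1.1 defines discontinuation as stopping before the planned duration, so it is an exception by nature, and 6.7.2 sets the minimum chiefly to prevent an early oral switch. The two instructions are unreconciled, but they are not in direct conflict.
- *That the chance of an event can be put in per cent.* Any such figure would rest wholly on an assumed rate.
- *That participants would go 48 h untreated.* The 48 h switch is a recommendation, and on the summary's listing Coartem lies outside the stop rule. It could be started earlier, although no text says so after an unplanned stop.
- *That the QTcF >500 ms stop in 8.4.5 has the same fault.* The first scheduled post-dose ECG follows the 24 h dose, so the three doses have by then been given, and QTcF above 500 ms is a genuine safety signal.
- *That an alternative parenteral antimalarial must be allowed.* Letting artesunate continue removes the gap without one.

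**Conclusion.** The concern holds in a limited form. For COVID-19 and prohibited-drug use, the mandatory stop in 9.1.1 covers control IV artesunate, neither trigger in itself requires that, and the plan permits no IV replacement in that arm. This rests on the protocol's own use of the term study treatment and on a literal reading of the mandatory wording. At most 96 planned participants are still exposed; the true number affected is probably very small and cannot be estimated from the documents. It is a cheap improvement for patient safety.

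**What to change.** In Protocol 9.1.1, split these two triggers by arm. For the artesunate arm, use the Table 16-2 wording that leaves continuation of IV artesunate to the investigator's benefit-risk assessment. For the cipargamin arm, stop cipargamin and switch to IV artesunate. Add the two reasons to the list in 6.2.1, because that list names neither and its safety clause covers only concerns due to cipargamin. No protection is lost: 9.1.1 already obliges the investigator to stop treatment judged harmful to the participant.

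The change has a downside that should be stated. SAP 2.4.2 classes IV artesunate given at the investigator's discretion to a cipargamin participant as rescue. Under SAP 2.5.3 rescue before the 12 h assessment is non-response, and under SAP Table 2-2 rescue before 48 h is not clinical success. A cipargamin participant switched for COVID-19 or a prohibited drug would therefore fail, while an artesunate participant with the same trigger could still succeed. The SAP should say so and list these cases with the reason for the switch. The amendment should also say whether they count toward the lack-of-efficacy pause rule in Table 3-1, which counts IV artesunate rescue under the protocol's criteria.

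The cost is amendment wording in 9.1.1 and 6.2.1, the Table 3-1 clarification, a sentence in the SAP and a reason flag in a listing. No extra participants or visits are needed.

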9.1.1.1 Replacement policy

For any cohort, enrollment of additional participants to the current cohort will be considered if there is less than the required number of evaluable participants. If the dose is considered unsuitable in the first few participants of the current cohort, enrollment of another set of new participants to the cohort to be treated with a different dose will be considered.

9.1.2 Withdrawal of informed consent

Participants may voluntarily withdraw consent to participate in the study for any reason at any time. Withdrawal of consent occurs only when a participant:

- Does not want to participate in the study anymore
- Does not allow further collection of personal data, and
- Does not want any further visits or assessments

In this situation, the investigator should make a reasonable effort (e.g. telephone, e-mail, letter) to understand the primary reason for the participant's decision to withdraw his/her consent and record this information.

Where consent to the use of personal and coded data is not required, participant therefore cannot withdraw consent. They still retain the right to object to the further use of personal data.

Study treatment must be discontinued and no further assessments conducted, and the data that would have been collected at subsequent visits will be considered missing.

Further attempts to contact the participant are not allowed unless safety findings require communicating or follow-up.

All efforts should be made to complete the assessments prior to study withdrawal. A final evaluation at the time of the participant's study withdrawal should be made as detailed in the assessment table ([Table 8-1](#) and [Table 8-2](#)).

Novartis will continue to keep and use collected study information (including any data resulting from the analysis of a participant's samples until the time of withdrawal) according to applicable law.

All biological samples not yet analyzed at the time of withdrawal will no longer be used, unless permitted by applicable law. They will be destroyed according to applicable legal requirements.

9.1.3 Lost to follow-up

For participants whose status is unclear because they fail to appear for study visits without stating an intention to discontinue or withdraw, the investigator must show "due diligence" by documenting in the source documents steps taken to contact the participant and/or care giver (accompanied with participant), e.g. dates of telephone calls, registered letters, etc. A participant should not be considered as lost to follow-up until due diligence has been completed or until the end of the study.

9.1.4 Early study termination by the sponsor

The study can be terminated by Novartis at any time for any reason. This may include reasons related to the benefit/ risk assessment of participating in the study, practical reasons (including

slow enrollment), or for regulatory or medical reasons. In taking the decision to terminate, Novartis will always consider the subject welfare and safety. Should early termination be necessary, participants must be seen as soon as possible and treated as prematurely withdrawn. The investigator may be informed of additional procedures to be followed in order to ensure that adequate consideration is given to the protection of the participant's interests. The investigator or sponsor, depending on the local regulation, will be responsible for informing IRBs/IECs of the early termination of the trial.

9.2 Study completion and post-study treatment

Each participant will be required to complete the study in its entirety and thereafter no further study treatment will be made available to them.

A participant will be considered to have completed the study when the participant has completed the last visit planned in the protocol, and any repeat assessments associated with this visit have been documented and followed-up appropriately by the investigator.

Participants who discontinue study drug and are put on rescue medication will be followed for the entire study duration (i.e., until study Day 29).

The investigator and/or referring physician must provide follow-up medical care for all participants who are prematurely withdrawn from the study, or must refer them for appropriate ongoing care.

An independent Data Monitoring Committee (DMC) will review participant safety at several time points and may recommend stopping a cohort/dose or the study early for safety reasons.

10 Safety monitoring and reporting

10.1 Definition of adverse events and reporting requirements

10.1.1 Adverse events

An adverse event (AE) is any untoward medical occurrence (e.g. any unfavorable and unintended sign [including abnormal laboratory findings], symptom or disease) in a participant or clinical investigation participant after providing written informed consent for participation in the study. Therefore, an AE may or may not be temporally or causally associated with the use of a medicinal (investigational) product.

The investigator has the responsibility for managing the safety of individual participant and identifying adverse events.

Novartis qualified medical personnel will be readily available to advise on trial related medical questions or problems.

The occurrence of adverse events must be sought by non-directive questioning of the participant at each visit during the study. Adverse events also may be detected when they are volunteered by the participant during or between visits or through physical examination findings, laboratory test findings, or other assessments.

Adverse events must be recorded under the signs, symptoms, or diagnosis associated with them, accompanied by the following information (as far as possible) (if the event is serious refer to [Section 10.1.2](#)):

1. The Common Toxicity Criteria (CTC) AE grade version 5

Adverse events will be assessed and graded according to the Common Terminology Criteria for Adverse Events (CTCAE) version.

2. its relationship to the study treatments (ie IV cipargamin or IV artesunate). If the event is due to lack of efficacy or progression of underlying illness (i.e. progression of the study indication) the assessment of causality will usually be 'Not suspected.' The rationale for this guidance is that the symptoms of a lack of efficacy or progression of underlying illness are not caused by the trial drug, they happen in spite of its administration and/or both lack of efficacy and progression of underlying disease can only be evaluated meaningfully by an analysis of cohorts, not on a single participant
3. its duration (start and end dates) or if the event is ongoing, an outcome of not recovered/not resolved must be reported
4. whether it constitutes a SAE (see [Section 10.1.2](#) for definition of SAE) and which seriousness criteria have been met
5. action taken regarding with study treatment

All adverse events must be treated appropriately. Treatment may include one or more of the following:

- Dose not changed
 - Drug interrupted/withdrawn
6. its outcome (i.e. recovery status or whether it was fatal)

Conditions that were already present at the time of informed consent should be recorded in medical history of the participant.

Adverse events (including lab abnormalities that constitute AEs) should be described using a diagnosis whenever possible, rather than individual underlying signs and symptoms.

Adverse event monitoring should be continued until the end of study visit.

Once an adverse event is detected, it must be followed until its resolution or until it is judged to be permanent (e.g. continuing at the end of the study), and assessment must be made at each visit (or more frequently, if necessary) of any changes in severity, the suspected relationship to the interventions required to treat it, and the outcome.

Information about adverse drug reactions for the investigational drug can be found in the [Investigator's Brochure](#). For comparator and oral standard of care treatments, safety-related information is listed in the product information.

Abnormal laboratory values or test results constitute adverse events only if they fulfill at least one of the following criteria:

- they induce clinical signs or symptoms
- they are considered clinically significant
- they require therapy

Clinically significant abnormal laboratory values or test results must be identified through a review of values outside of normal ranges/clinically notable ranges, significant changes from baseline or the previous visit, or values which are considered to be non-typical in participants with the underlying disease.

